2. INTRODUCTION AND RATIONALE

2.1. Temporal changes in fluid therapy in critically ill invasively ventilated patients

Intravenous fluid is among the most prescribed medications in the intensive care unit (ICU). Most is used intentionally, to improve hemodynamics in patients with hypotension or hypoperfusion, and to compensate for lost fluids (1). A smaller amount is administered unintentionally, as a vehicle for medication or to maintain catheter patency (2). Intravenous fluid administration was once considered to be ‘harmless’. However, in recent years it became clear that fluid therapy has important side-effects. The paradigm of ‘liberal fluid administration’ in critically ill patients has been challenged, and novel concepts such as ‘restricted fluid administration’, defined as minimizing fluid intake while maintaining organ perfusion (3), ‘timely deresuscitation’, defined as early and active removal of fluid after initial resuscitation (4), and ‘fluid tolerance’, defined as the degree to which a patient can tolerate fluid administration without causing organ dysfunction (5-7), were introduced.

As there are complex interactions between invasive ventilation and fluid status, fluid therapy in invasively ventilated patients is even more challenging. Invasive ventilation disrupts fluid homeostasis and predisposes to hemodynamic intolerance of hypovolemia (8). Conversely, hypervolemia can lead to pulmonary edema resulting in an impaired gas-exchange and worsened pulmonary compliance, jeopardizing lung-protective ventilation (8).

The type of fluid has also been subject of discussion. While initially thought to be beneficial, synthetic colloidal solutions not only have no benefit over crystalloid solutions (9-11), but even cause harm (12). Albumin solutions also have no benefit in unselected critically ill patients, and may only improve outcome in patients with septic shock but are considered harmful in patients with traumatic brain injury (13, 14). Crystalloid solutions are now first choice (15). While balanced crystalloid solutions were initially thought to prevent kidney injury (16), they do not clearly improve outcomes and may even be harmful for traumatic brain injury patients (17, 18).

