5.5. Sample size calculation

No formal sample size calculation is necessary for the primary endpoint. However, for investigating associations of aspects of fluid and vasopressor therapy with mortality using logistic regression and adjusting for a limited set of pre-specified confounders, we estimate to need 150 ‘events’ using the 10 event per variable rule of thumb. As fluid and vasopressor management is particularly important in patients with acute respiratory distress (ARDS), we will need at least 150 events in this subgroup. With an incidence of ARDS of approximately 20% and a mortality rate of 30%, we estimate to need 2500 patients to have 150 events in patients with ARDS (37). Assuming that a participating ICU has 50 unique admissions in 4 weeks on average, of which 25% is invasively ventilated for > 24 hours, we expect to need a minimum of 200 participating ICUs (38-40).

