6. METHODS

6.1. Study parameters

6.1.1. Primary parameter

- Quantity, timing and type of intravenous fluids administered.

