6.1.2. Secondary study parameters

- Time of start of vasopressors;
- Route of administration for vasopressors (i.e. central vs. peripheral route);
- Types of vasopressor used;
- Daily urine output;
- Cumulative fluid balance;
- Timing of start, type and infusion time (i.e. bolus vs. continuous infusion) of administered diuretic;
- Incidence of atrial arrhythmias;
- Incidence of acute respiratory distress syndrome (ARDS)
- Incidence of renal replacement therapy;
- Incidence of persistent renal dysfunction, defined as the need for renal replacement therapy at ICU discharge;
- ICU length of stay, defined as the time between ICU admission and discharge or death;
- Hospital length of stay, defined as the time between hospital admission and discharge or death;
- Duration of ventilation, defined as the time between initiation of invasive ventilation and successful liberation of ventilation.
- Ventilator-free days and alive at day 28, defined as 28 - x if successfully liberated from ventilation x days after initiation. If subject dies within 28 days ventilator-free days is set to 0;
- All-cause ICU mortality, defined as any death during ICU stay;
- All-cause in-hospital mortality at day 28, defined as any death during hospital stay before or on study day 28;
- All-cause in-hospital mortality at day 60, defined as any death during hospital stay before or on study day 60;
- All-cause in-hospital mortality at day 90, defined as any death during hospital stay before or on study day 90;

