- Heart rate, beats/min, at a convenient fixed time point;
- Atrial fibrillation or flutter during the last day, yes/no;
- Arterial or venous lactate, if measured, mmol/L , highest and lowest value;
- (Central) venous oxygen saturation ($S(c)VO_2$), mmol/L , if measured, highest and lowest value;
- Arterial partial pressure of oxygen (PaO_2), kPa or mmHg , at a convenient fixed time point;
 - (if no PaO_2 is known) Peripheral arterial oxygen saturation (SpO_2), percentage, at a convenient fixed time point;
- Inspired oxygen fraction, %, at time of PaO_2 or (if no PaO_2 is known) SpO_2 ;
- Suspected or confirmed infection that causes organ dysfunction (sepsis) yes/no;
- Was there new-onset (<7 days) respiratory symptoms, or acute worsening of respiratory symptoms?, yes/no, if yes;
- Are there bilateral opacities on chest imaging (including lung ultrasound), yes/no;
- If there was hypoxemia, was the hypoxemia explained by cardiac failure, yes/no?

- Richmond Agitation Sedation Scale (RASS), highest value of this day after intubation; and
- Sequential Organ Failure Assessment (SOFA) score.

C. Daily on day 1 and day 2;

- Type, volume, ml, and rate, ml/min, of each separate fluid infusion (including medication and parenteral nutrition);
- Type and volume of oral fluids;
- Anuria \geq 12 hours?, yes/no;
- Urine output, ml, over 24 hours;
- Extracorporeal life support, venoarterial/venovenous/no;
- Renal replacement therapy, yes/no, if yes;
 - Volume extracted by ultrafiltration, ml, over 24 hours;
- Cumulative fluid balance, ml;
- Loop diuretics given, yes/no, if yes;
 - Furosemide, yes/no, if no;
 - (if no furosemide used) Bumetanide, yes/no, if no;
 - (if no bumetanide or furosemide used) Torasemide, yes/no;
 - (if no Torasemide, bumetanide, furosemide used) Edecrin, yes/no;
 - Additional diuretic given (thiazide, carbonic anhydrase inhibitor or mineralocorticoid antagonist), yes/no;
- Serum creatinine, $\mu\text{mol/L}$ or mg/dL , at a convenient fixed time point;
- Serum hemoglobin, $\mu\text{mol/L}$ or mg/dL , at a convenient fixed time point;
- Serum albumin, at a convenient fixed time point;
- Vasopressors given, yes/no, if yes;
 - Time between ICU admission and initiation of vasopressors, only if not initiated on day 0, hours;
 - Drug(s) used as vasopressor;
- MAP, mmHg, at a convenient fixed time point;
- Heart rate, beats/min, at a convenient fixed time point;
- Atrial fibrillation or flutter during the last day, yes/no;

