8.2. Plan of analysis

Subjects that are transferred to another ICU in the first three calendar days of ICU admission will be excluded from analysis. Subjects that are transferred to another ICU after the first three calendar days, but before seven days are excluded from analysis of the secondary endpoints. Patients admitted due to pancreatitis, burns, diabetic ketoacidosis, severe rhabdomyolysis and sub-arachnoid bleeding will be analyzed separately and excluded from analysis if less than 30 subjects are included in each category. Subjects diagnosed with sepsis or ARDS during the first three calendar days of ICU admission will be part of a subgroup analysis. Associations with outcomes will be assessed through regression modelling. Time to event variables are analyzed using Cox regression and visualized by Kaplan–Meier plots. For each analysis proposed, a complete statistical analysis plan will be prepared, finalized and made available before starting the analyses. Statistical analyses are conducted using R (www.r-project.org). A *P*–value of less than 0.05 is considered statistically significant.

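### The only item on the cause of hypoxaemia asks about cardiac failure and not fluid overload, so overload oedema may not be separable from ARDS in a study of fluid therapy

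*Protocol*

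**What the plan says.** Protocol section 6.2.3, lists B (day 0) and C (days 1 and 2), holds the items from which ARDS could be recognised:

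- onset: "Was there new-onset (<7 days) respiratory symptoms, or acute worsening of respiratory symptoms?, yes/no, if yes";
- imaging: "Are there bilateral opacities on chest imaging (including lung ultrasound), yes/no", with no question about the cause of the opacities;
- oxygenation: PaO₂, or SpO₂ if PaO₂ is not known, with the inspired oxygen fraction;
- cause: "If there was hypoxemia, was the hypoxemia explained by cardiac failure, yes/no".

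The cause item has the same wording on all three days. List D (days 3 to 7 and the days before intubation) has no onset, imaging or cause item. List E (events) asks about acute kidney injury and rhabdomyolysis but not ARDS.

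Three parts of the protocol depend on the ARDS label. Section 6.1.2 lists ARDS incidence as a secondary parameter. Section 8.2 plans a subgroup: "Subjects diagnosed with sepsis or ARDS during the first three calendar days of ICU admission will be part of a subgroup analysis". Section 5.5 bases the sample size on it: "As fluid and vasopressor management is particularly important in patients with acute respiratory distress (ARDS), we will need at least 150 events in this subgroup".

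The primary parameter in section 6.1.1 is "Quantity, timing and type of intravenous fluids administered". Section 2.1 says that "hypervolemia can lead to pulmonary edema resulting in an impaired gas-exchange and worsened pulmonary compliance".

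**The concern.** Section 2.1 names a route from fluid to hypoxaemia that needs no cardiac failure. Section 6.2.3 then collects nothing that identifies patients who took that route. The unrecorded alternative explanation is an effect of the exposure being studied, so any mislabelling would be more likely in patients who received more fluid and would not be random noise.

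Two results are exposed. Recorded ARDS incidence could be too high. The ARDS subgroup could also contain patients who entered it partly because of the fluid they received, which complicates reading fluid-outcome associations inside it. The gap lies in data capture: a statistical analysis plan can write rules only on fields that exist, and it cannot recover an attribution that no site was asked to make.

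**Working it through.** **1. Reading the items together.** Take a patient without cardiac failure who receives a large fluid volume and develops pulmonary oedema.

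| Item | Answer in overload oedema | Answer in ARDS |
|---|---|---|
| New or worse respiratory symptoms | can be yes | yes |
| Bilateral opacities | can be yes | yes |
| Low oxygenation | can be yes | yes |
| Explained by cardiac failure | no | no |

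The four answers can coincide, and no other field asks whether overload explained the hypoxaemia.

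**2. The plan's own figures (section 5.5).** Inputs: 150 events, ARDS incidence 20%, mortality 30%, 50 admissions per ICU in four weeks, 25% of them ventilated for more than 24 hours.

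- Patients: 150 / (0.20 × 0.30) = 2500. This matches the plan.
- ICUs: 2500 / (50 × 0.25) = 2500 / 12.5 = 200. This matches the plan.
- Expected ARDS patients: 2500 × 0.20 = 500; patients without ARDS: 2000.

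The sample size arithmetic is correct. The question is what the 500 would contain.

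**3. Illustration A: true incidence is 20% and overload cases are added.** Let g be the share of the 2000 patients without ARDS who have overload hypoxaemia and meet every other item. The documents give no value for g; the range is an assumption. Recorded incidence = 0.20 + 0.80g; false share of the subgroup = 0.80g / (0.20 + 0.80g).

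| g | Patients added | Recorded incidence | False share of subgroup |
|---|---|---|---|
| 1% | 20 | 20.8% | 20/520 = 3.8% |
| 2.5% | 50 | 22.0% | 50/550 = 9.1% |
| 5% | 100 | 24.0% | 100/600 = 16.7% |
| 10% | 200 | 28.0% | 200/700 = 28.6% |

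**4. Illustration B: the recorded 20% already contains overload cases.** Let f be the overload share of the 500, also an assumption, with mortality held at 30%. ARDS deaths without overload cases = 150(1 − f); patients needed for 150 such deaths = 2500 / (1 − f), rounded up; ICUs = that number before rounding / 12.5, rounded up.

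| f | Overload cases | ARDS deaths | Patients for 150 | ICUs |
|---|---|---|---|---|
| 5% | 25 | 142.5 | 2632 | 211 |
| 10% | 50 | 135 | 2778 | 223 |
| 20% | 100 | 120 | 3125 | 250 |
| 30% | 150 | 105 | 3572 | 286 |

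**5. Subgroup mortality.** This moves only if overload patients die at a different rate. With g = 5% and an assumed mortality of 15% in them: (500 × 0.30 + 100 × 0.15) / 600 = 165/600 = 27.5%. With 45%: (150 + 45) / 600 = 32.5%. The sign depends on a rate that the documents do not give.

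**The case against.** **The protocol writes no ARDS rule.** This stands. Section 6.1.2 lists the endpoint without an algorithm, section 8.2 speaks of subjects diagnosed with ARDS, and it promises a full analysis plan before each analysis. A reader might infer that overload cases are counted as ARDS. That is an inference from these being the only ARDS items collected, so the supportable statement is that such cases may not be separable.

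**Other fields bear on overload.** This stands in part. Fluid volumes, cumulative balance, urine output, ultrafiltration and diuretics are recorded and allow indirect sensitivity analyses, such as leaving out cases with a high balance. None records whether overload explained the hypoxaemia, and defining ARDS by fluid balance would put the exposure into the definition.

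**The link between fluid and ARDS is not circular.** This stands. A reader might infer that an association would arise by definition. Fluid volume is not part of any ARDS item; fluid that causes oedema, opacities and hypoxaemia has a real effect, and only the label is in doubt.

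**The LMIC-HIC comparison is not shown to be distorted.** This stands. Sections 3.1 and 3.2 state that comparison for fluid and vasopressor therapy, not for ARDS incidence. The item does not touch how therapy is measured, and the primary parameter is unaffected.

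**Sites may read cardiac failure to include overload.** The wording does not say so. With at least 200 ICUs in 30 countries expected (section 5.1), differing readings would add variation between sites.

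**Conclusion.** The point holds as a gap in data capture. The protocol itself describes fluid-caused pulmonary oedema, studies fluid as its exposure, and asks only about cardiac failure as a cause of hypoxaemia. If ARDS is derived from the collected items, overload cases that meet the other items can only raise recorded incidence, and subgroup entry can depend partly on fluid volume.

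The size is not known. Figures from 20.8% to 28.0% rest on an assumed 1% to 10% of patients without ARDS being mislabelled. The 25 to 150 overload cases among 500 rest on an assumed 5% to 30% share. A reader might go further and infer that the fluid-mortality association in the subgroup is biased in a known direction, or that the sample size is wrong. The documents support neither: the direction depends on outcome rates that are not given, and the 2500 patients and 200 ICUs follow from the stated inputs.

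**What to change.** In section 6.2.3, lists B and C, keep the cardiac failure item exactly as worded. Beside it, on days 0, 1 and 2, add a second yes/no item of the same form that asks whether fluid overload explained the hypoxaemia. Two separate items are better than one merged single-choice item, because both causes can be present in the same patient and rewording the existing item could change who answers yes to it.

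Report ARDS incidence and the ARDS subgroup analysis with overload-explained cases excluded and, as a sensitivity analysis, with them included. Both are needed: data are transcribed from charts, so the overload judgement may itself be influenced by the recorded volumes, and exclusion alone could remove high-volume patients because of their exposure.

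The cost is one more chart-based judgement per patient on each of three days, with no extra test or visit. Excluding cases may leave fewer than 150 deaths in that version of the subgroup analysis, as illustration B shows. The item has to be in the CRF before data are entered.

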1. SUMMARY

Rationale

The worldwide practice of fluid and vasopressor therapy in critically ill invasively ventilated patients is uncertain. Indeed, it is unclear whether there is a difference in fluid and vasopressor therapy in these patients between Low- and Middle-income Countries (LMICs) and High-income Countries (HICs).

Objective

To determine various aspects of fluid and vasopressor therapy in critically ill invasively ventilated patients in LMICs and HICs.

Hypothesis

There is substantial worldwide variation in practice of fluid and vasopressor therapy in critically ill invasively ventilated patients.

Study design

International, multicenter, observational study in critically ill invasively ventilated patients; data are captured during a predefined period per geographic region or country.

Study population

Critically ill invasively ventilated patients.

Main study parameter/endpoint

The primary outcome is a composite of various aspects of fluid therapy, including total volumes of types of fluids administered in the first three days after start of invasive ventilation and total volume of fluids infused in the first seven days after start of invasive ventilation. Secondary outcomes include timing of start, type, and duration of continuous administration of vasopressors; timing of start, infusion time and types of administered diuretics; daily urine output and cumulative fluid balances; and typical ICU outcomes, like duration of ventilation, lengths of stay in ICU and hospital, and mortality in the ICU and hospital, and at day-28, -60 and -90.

Nature and extent of the burden and risks associated with participation, benefit and group relatedness

Because of the observational design of the study using routinely collected data, there is no additional burden for the patient. Collection of data from ICU charts or electronic medical records systems is of no risk to the patients.

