6.2. Study procedures

Patients in participating centers are screened on a daily basis. Eligible patients are included during the 28–day observation period, from Monday at 8:00 AM to the Monday four weeks later at 7:59 AM (in time zones of the participating centers). The timing of the 28–day observation period will be flexible for participating centers and determined at a later stage together with the international study–coordinator and each national investigator. Times points of data collection:

- Demographic and baseline data are collected from the clinical files – at ICU admission;
- Types, quantities, of administered fluids– during the first three calendar days with high-granularity. From day 4-7 lower granularity data concerning the total volume of infused fluids will be collected;
- Types and modalities of administration of vasopressors – over a maximum of seven days of ICU admission;
- Vital signs, laboratory results and limited treatment parameters are collected – once daily for a maximum of seven days;
- Cumulative fluid balance – calculated once a day on a time point convenient per each center for a maximum of seven days; and
- Outcomes – recorded at 90 days, the day of death or hospital discharge, whichever comes first.

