6.2.3. Data to be collected

The following data will be collected for all enrolled patients admitted to ICU during the screening period. Day 0 is defined as the day of initiation of invasive ventilation. Day 1 is defined as the first full calendar day after initiation of invasive ventilation. In patients that are not invasively ventilated at ICU admission day -3 to -1 are defined as the days before intubation but after ICU admission.

A. At ICU admission;

- Gender, male/female/other;
- Age, years;
- Weight, kg;
- Length, cm;
- Ethnicity, Black, East Asian, Indigenous (First Nations, Inuk/Inuit, Métis), Latin American, Middle Eastern, South Asian, Southeast Asian, White;
- Reason for ICU admission;
- Traumatic brain injury?;
- Sub-arachnoid hemorrhage?
- Date of ICU admission;
- Date of start of invasive ventilation;
- Did the patient receive non-invasive ventilation or high-flow nasal oxygen prior to intubation, if so: on which day?;
- Serum creatinine, $\mu\text{mol/L}$ or mg/dL , lowest in the last year, if available; and
- If the reason for ICU admission was burns: what was the cause of the burn and how much total body surface area is affected by the burns
- If the reason for ICU admission was sepsis, what was the focus of the sepsis (e.g. respiratory, abdominal)

B. On day 0;

- Type and volume, ml, of each fluid infusion (including medication and parenteral nutrition);
- Type and volume of oral fluids;
- Anuria ≥ 12 hours?, yes/no;
- Urine output, ml, over 24 hours;
- Extracorporeal life support, venoarterial/venovenous/no;

- Renal replacement therapy, yes/no, if yes;
 - Volume extracted by ultrafiltration, ml, over 24 hours;
- Cumulative fluid balance, ml;
- Loop diuretics given, yes/no, if yes;
 - Furosemide, yes/no, if yes;
 - (if no furosemide used) Bumetanide, yes/no, if yes;
 - (if no bumetanide or furosemide used) Torasemide, yes/no, if yes;
 - (if no Torasemide, bumetanide, furosemide used) Edecrin, yes/no;
- Additional diuretic given (thiazide, carbonic anhydrase inhibitor or mineralocorticoid antagonist), yes/no;
- Serum creatinine, $\mu\text{mol/L}$ or mg/dL , at a convenient fixed time point;
- Serum hemoglobin, $\mu\text{mol/L}$ or mg/dL , at a convenient fixed time point;
- Serum albumin, at a convenient fixed time point;
- Vasopressors initiated, yes/no, if yes;
 - Time between ICU admission and initiation of vasopressors, hours;
 - Drug(s) used as vasopressor;
- Mean arterial pressure (MAP) mmHg, at a convenient fixed time point;

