- Arterial or venous lactate, mmol/L , at a convenient fixed time point;
- Serum sodium, mmol/l , at a convenient fixed time point;

- Serum chloride, mmol/l, at a convenient fixed time point;
-
- S(c)VO₂, mmol/L, highest and lowest value;
- PaO₂, kPa or mmHg, at a convenient fixed time point;
- (if no PaO₂ is known) Peripheral arterial oxygen saturation (SpO₂), percentage, at a convenient fixed time point;
- Inspired oxygen fraction, %, at time of PaO₂ or (if no PaO₂ is known) SpO₂;
- Was there new-onset (<7 days) respiratory symptoms, or acute worsening of respiratory symptoms?, yes/no, if yes;
- Are there bilateral opacities on chest imaging (including lung ultrasound), yes/no;
- If there was hypoxemia, was the hypoxemia explained by cardiac failure, yes/no?
- Richmond Agitation Sedation Scale (RASS), highest value of the day; and
- SOFA score.

D. Daily on day 3 to 7 or ICU discharge; and on day -1, day -2 and day -3;

- Total volume of infused fluid, ml, over 24 hours
- Cumulative fluid balance, ml, over 24 hours;
- Urine output, ml, over 24 hours;
- Extracorporeal life support, venoarterial/venovenous/no;
- Renal replacement therapy, yes/no, if yes;
 - Volume extracted by ultrafiltration, ml, over 24 hours;
- Loop diuretics given, yes/no, if yes;
 - Furosemide, yes/no, if no;
 - (if no furosemide used) Bumetanide, yes/no, if no;
 - (if no bumetanide or furosemide used) Torasemide, yes/no;
 - (if no Torasemide, bumetanide, furosemide used) Edecrin, yes/no;
 - Additional diuretic given (thiazide, carbonic anhydrase inhibitor or mineralocorticoid antagonist), yes/no;
- Serum creatinine, µmol/L or mg/dL, at a convenient fixed time point;
- Serum hemoglobin, µmol/L or mg/dL, at a convenient fixed time point;
- Serum albumin, at a convenient fixed time point;
- Vasopressors used, yes/no, if yes;
 - Drug(s) used as vasopressor;

- MAP, mmHg, at a convenient fixed time point;
- Heart rate, beats/min, at a convenient fixed time point
- Atrial fibrillation or flutter during the last day, yes/no;
- Arterial or venous lactate, mmol/L, at a convenient fixed time point;
- Serum sodium, mmol/l, at a convenient fixed time point;
- Serum chloride, mmol/l, at a convenient fixed time point;
- PaO₂, kPa or mmHg, at a convenient fixed time point;
- (if no PaO₂ is known)) Peripheral arterial oxygen saturation (SpO₂), percentage, at a convenient fixed time point;
- Inspired oxygen fraction, %, at time of PaO₂ or (if no PaO₂ is known) SpO₂; and
- SOFA score.

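### The fluid-balance item does not say whether it is a running total or a 24-hour figure, and the day numbering of sections 6.2 and 6.2.3 cannot be reconciled

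*Protocol*

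**What the plan says.** **Fluid balance.** Section 6.1.2 lists cumulative fluid balance as a secondary parameter, without formula or start point. In section 6.2.3, block B (day 0) and block C (days 1 and 2) request "Cumulative fluid balance, ml" with no time window. Block D requests "Cumulative fluid balance, ml, over 24 hours". Section 6.2 says the balance is "calculated once a day on a time point convenient per each center for a maximum of seven days".

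**Study days.** Section 6.2.3 states "Day 0 is defined as the day of initiation of invasive ventilation" and "Day 1 is defined as the first full calendar day after initiation of invasive ventilation". Each separate infusion is recorded in blocks B and C. Only a total infused volume is recorded in block D, which is headed "D. Daily on day 3 to 7 or ICU discharge; and on day -1, day -2 and day -3".

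**Windows.** The summary defines part of the primary outcome as "total volume of fluids infused in the first seven days after start of invasive ventilation", next to a three-day total by fluid type. Section 6.2 puts the detailed fluid data in the opening three calendar days and then says: "From day 4-7 lower granularity data concerning the total volume of infused fluids will be collected".

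**The concern.** A balance is either accumulated from some origin or it covers one 24-hour period. The block D label claims both, and it differs from the label used on days 0 to 2. Two careful sites could follow the form and enter different quantities. The study expects at least 200 ICUs in 30 countries, so the form's wording is the main safeguard.

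The introduction (section 2.2) cites links between cumulative balance and mortality, duration of ventilation and kidney dysfunction. Section 3.1 aims to relate aspects of fluid therapy to outcome. The balance is therefore a likely exposure in those models, and a mixture of two quantities under one variable name would distort them.

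The day numbering bears on the primary outcome: the protocol does not say which study days make up the seven-day total, and its two sections on data collection imply different sets.

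**Working it through.** **1. What the balance entry can mean.** The protocol gives no daily balances, so the values here are assumptions.

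- Constant +1000 ml on each of days 0 to 7. Day-7 entry as a running total from day 0: 8 × 1000 = 8000 ml. As a 24-hour balance: 1000 ml.
- Early gain, later removal: +1500, +1000, +500, +250, 0, −250, −250, −500 ml on days 0 to 7. Running total on day 7: 1500 + 1000 + 500 + 250 + 0 − 250 − 250 − 500 = +2250 ml. 24-hour balance: −500 ml. Even the sign differs.
- Start point: a patient admitted three days before intubation, +1000 ml each day. Running total on day 2 from the day of intubation: 3 × 1000 = 3000 ml. From ICU admission (days −3 to 2): 6 × 1000 = 6000 ml.

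**2. Whether the balance can be rebuilt from other items in section 6.2.3.**

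| Component | Days 0–2 (B, C) | Days 3–7 and −3 to −1 (D) |
|---|---|---|
| Infused volume | each infusion | daily total |
| Oral fluids | yes | no |
| Urine output | yes | yes |
| Ultrafiltrate, if on renal replacement | yes | yes |
| Other losses | no | no |

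In block D, both oral intake and other losses are missing. The site's own entry is the only source of the full balance on those days.

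**3. Counting the days.** The stated figure is seven. Block B gives day 0 (1 record), block C days 1 and 2 (2 records), block D days 3 to 7 (5 records): 1 + 2 + 5 = 8. The seven is not reproduced. The pre-intubation days would add up to three more.

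**4. Whether any reading of section 6.2 matches section 6.2.3.**

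| Reading of section 6.2 | Detailed days | Lower-granularity days | Conflict with 6.2.3 |
|---|---|---|---|
| Study-day labels, first three = 0–2 | 0, 1, 2 | 4–7 | day 3 belongs to neither group |
| Study-day labels, first three = 1–3 | 1, 2, 3 | 4–7 | day 0 left out; day 3 detailed instead of a total |
| Ordinal count, 1st to 7th day = 0–6 | 0, 1, 2 | 3–6 | day 7 lies outside the window |

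Each reading leaves one conflict or more.

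**5. What the choice of window changes.** Let day 0 contain h hours after intubation, assumed between 1 and 24.

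- Days 0–7: h + 168 = 169 to 192 h
- Days 0–6: h + 144 = 145 to 168 h
- Days 1–7: 168 h
- Days 0–2: h + 48 = 49 to 72 h

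With equal daily volumes and a full day 0, an eight-day total is 8/7 = 1.14 times a seven-day total. This is an illustration: volumes usually need not be equal across days, and the disputed day may hold more or less than an average share.

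**The case against.** The strongest reply is that the numbering problem is one slip seen from two sides. If section 6.2 counts ordinally, the switch to lower granularity agrees with section 6.2.3 and only day 7 is left over. If it uses the study-day labels, the seven days could be days 1 to 7 after a partial day 0. Volumes are recorded daily on days 0 to 7, so any seven-day total can still be computed, and section 8.2 promises an analysis plan that can name the days. All of this stands. It makes the window point a matter of reconciling text and not a loss of data.

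On the balance, if every site read the labels literally and used the same start, the day-2 running total plus five 24-hour balances would give the right sum: 3 + 5 = 8 L in the constant example. That is correct, but nothing ensures a literal reading of a self-contradictory label, and no start is stated. An analysis plan written later cannot recover which quantity a site entered.

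Some stronger inferences are tempting but unsupported:

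- **Running totals will be added up as if they were daily values.** No section prescribes such a sum.
- **One day in seven or eight (12.5 to 14%) is the maximum error in the fluid total.** It holds only for equal daily volumes and a full day 0, so it is not a bound.
- **The entry criterion of more than 24 hours of ventilation cannot be checked, because only dates are recorded.** Local investigators screen daily with access to the chart. From dates alone, an uninterrupted first episode is ambiguous only when extubation falls on the next calendar day.
- **The error is confounded with country.** Reading times vary by centre, but nothing in the protocol shows that they follow country or income group.

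**Conclusion.** The point holds in two parts of unequal weight.

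The fluid-balance item is wrong as written. Its meaning changes between blocks, its block D label is contradictory, its origin is undefined and its reading time is left to the centre. The possible discrepancy is large (8 L against 1 L on day 7 at an assumed +1 L per day) and may include a change of sign. The litre values rest on assumed balances; the ambiguity itself does not. It has to be settled at data entry, because the other block D items cannot reproduce the balance. It concerns a secondary parameter, not the primary one.

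The window inconsistency is also real: eight daily records against a maximum of seven, and a switch at day 3 or day 4 depending on the section. It does touch the primary total, but it is lighter, since the daily volumes allow any seven-day window to be formed. The sample size is unaffected.

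**What to change.** 1. Replace the balance item in blocks B, C and D with one item: the 24-hour fluid balance, for the same study-day window as volumes and urine output, on every day from −3 to 7. Derive the cumulative balance centrally from one stated start day.
2. Use the section 6.2.3 day numbering in section 6.2 as well, so that the granularity switch and the maximum number of daily records agree.
3. State that the three-day total covers days 0 to 2, and name the days of the seven-day total. Days 0 to 6 or days 1 to 7 would both serve; what matters is that one is chosen.
4. Optionally, record the clock time of intubation, so that the partial day 0 can be expressed per hour observed.

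The cost is relabelling one item in three eCRF blocks, correcting one or two sentences, and one optional time field.
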